7.7 Treatment of Overdose

The effects of overdose of AMG 598 are not known. Consult the investigator and Amgen Medical Monitor immediately if an overdose is suspected, or subject experiences signs or symptoms of an adverse event related to a potential overdose.

For liraglutide, refer to the approved product label for advice on overdose and report to Amgen Medical Monitor.

7.8 Prior and Concomitant Treatment

7.8.1 Prior Treatment

Prior therapies that were being taken/used prior to enrollment will be collected per the timeframes defined in Sections 6.1 and 6.2.

7.8.2 Concomitant Treatment

Throughout the study, investigators may prescribe any concomitant medications or treatments deemed necessary to provide adequate supportive care except for those listed in Section 7.1.7.

Concomitant therapies are to be collected from enrollment through the end of study. For all concomitant therapies, collect therapy name, indication, dose, unit, frequency, route, start date and stop date.

8. Discontinuation Criteria

Subjects have the right to withdraw from investigational product and/or other protocol-required therapies, protocol procedures, or the study as a whole at any time and for any reason without prejudice to their future medical care by the physician or at the institution.

The investigator and/or sponsor can decide to withdraw a subject(s) from investigational product and/or other protocol-required therapies, protocol procedures, or the study as a whole at any time prior to study completion for the reasons listed in Sections 8.1, 8.2.1, and 8.2.2.

8.1 Discontinuation of Study Treatment

Subjects (or a legally acceptable representative) can decline to continue receiving investigational product and/or other protocol-required therapies or procedures at any time during the study but continue participation in the study. If this occurs, the investigator is to discuss with the subject the appropriate processes for discontinuation from investigational product or other protocol-required therapies and must discuss with the subject the possibilities for continuation of the Schedule of Activities (see Section 2.2) including different options of follow-up (eg, in person, by phone/mail, through family/friends, in correspondence/communication with other treating physicians, from the review of medical records) and collection of data, including endpoints, adverse events, as applicable and must document this recommendation in the subject's medical records. Subjects who have discontinued investigational product and/or other protocol-required therapies or procedures should not be automatically removed from the study. Whenever safe and feasible, it is imperative that subjects remain on-study to ensure safety surveillance and/or collection of outcome data.

Subjects may be eligible for continued treatment with Amgen investigational product(s) and/or other protocol-required therapies by a separate protocol or as provided for by the local country's regulatory mechanism, based on parameters consistent with Section 12.3

Approvec

Reasons for removal from protocol-required investigational product(s) or procedural assessments include any of the following:

- Decision by Sponsor
- Lost to follow-up
- Death
- Ineligibility determined
- Protocol deviation
- Non-compliance
- Adverse event
- Subject request
- Pregnancy
- Protocol-specified criteria (Hepatotoxicity Stopping Rules and Mental Health Criteria Stopping Rules); see Section 7.4 and Section 12.8

8.2 Discontinuation From the Study

Withdrawal of consent for a study means that the subject does not wish to receive further protocol-required therapies or procedures, and the subject does not wish to or is unable to continue further study participation. Subject data up to withdrawal of consent will be included in the analysis of the study, and where permitted, publicly available data can be included after withdrawal of consent. The investigator is to discuss with the subject appropriate procedures for withdrawal from the study and must document the subject's recommendation to withdraw in the subject's medical records.

Whenever safe and feasible it is imperative that subjects remain on-study to ensure safety surveillance and/or collection of outcome data. The investigator must document the level of follow-up that is agreed to by the subject.

If a subject withdraws from the study, he/she may request destruction of any samples taken and not tested, and the investigator must notify Amgen accordingly (see Section 12.6 for further details).

8.2.1 Reasons for Removal From Run In

Reasons for removal of a subject from the run-in period are:

- Decision by Sponsor
- Lost to follow-up
- Death
- Ineligibility determined
- Protocol deviation

- Non-compliance •
- Adverse event •
- Subject request
- Pregnancy
- Protocol-specified criteria (Part 2 inclusion/exclusion criteria); see Section 6.3 and 6.4

Subjects removed from run-in will be removed from study.

8.2.2 **Reasons for Removal From Study**

Reasons for removal of a subject from the study are:

- Decision by Sponsor •
- Withdrawal of consent from study
- Death
- Lost to Follow up •
- Protocol-specified criteria (Part 2 inclusion/exclusion criteria); • see Section 6.3 and 6.4

8.3 Lost to Follow-up

A subject will be considered lost to follow-up if he or she repeatedly fails to return for scheduled visits and is unable to be contacted by the study site.

The following actions must be taken if a subject fails to return to the clinic for a required

study visit:

- The site must attempt to contact the subject and reschedule the missed visit as soon as possible and counsel the subject on the importance of maintaining the assigned visit schedule and ascertain whether or not the subject wishes to and/or is able to continue in the study.
- In cases in which the subject is deemed lost to follow-up, the investigator or • designee must make every effort to regain contact with the subject (where possible, 3 telephone calls and, if necessary, a certified letter to the subject's last known mailing address or local equivalent methods). These contact attempts are to be documented in the subject's medical record.
- If the subject continues to be unreachable, he/she will be considered to have withdrawn from the study with a primary reason of lost to follow-up.
- For subjects who are lost to follow-up, the investigator can search publicly available • records where permitted to ascertain survival status. This ensures that the data set(s) produced as an outcome of the study is/are as comprehensive as possible.

9. **Study Assessments and Procedures**

Study procedures and their time points are summarized in the Schedule of Activities (see Table 2-1 to Table 2-3).

As protocol waivers or exemptions are not allowed if an enrolled subject is subsequently determined to be ineligible for the study, this must be discussed with the sponsor immediately upon occurrence or awareness to determine if the subject is to continue or discontinue study treatment.

Adherence to the study design requirements, including those specified in the Schedule of Activities, is essential and required for study conduct.

9.1 General Study Periods

9.1.1 Screening, Enrollment and/or Randomization

Informed consent must be obtained before completing any study specific screening procedure or discontinuation of standard therapy for any disallowed therapy. For subjects consenting to participate in cohorts 1-6, after the subject has signed the informed consent form, they will be assigned a subject ID. For subjects consenting to participate in Cohort 7, after the subject has signed the informed consent form, the site will register the subject in the IVRS/IWRS and screen the subject in order to assess eligibility for participation. The screening window is up to 28 days prior to first dose of AMG 598/placebo or, for cohort 7, the placebo at the start of the run-in.

All screening evaluations must be completed and reviewed to confirm that potential subjects meet all eligibility criteria. The investigator will maintain a screening log to record details of all subjects screened and to confirm eligibility or record reasons for screening failure, (see Section 6.6) as applicable.

If a subject has not met all eligibility criteria at the end of the screening period, the subject will be registered as a screen fail. Screen fail subjects may be eligible for re-screening 1 time, after Sponsor approval.

If the subject meets eligibility criteria but is not enrolled within the 28 day screening period, a new 28-day screening window may begin for an open cohort and all screening procedures should be repeated. This subject is not registered as a screen fail.

Once the subject is registered as rescreened, a new 28-day screening window will begin. Subjects will retain the same subject identification number assigned at the original screening. If the rescreening period begins more than 28 days after the original signing of the informed consent form, all screening procedures, including informed consent, must be repeated.

9.1.2 Treatment Period and Follow up

Visits will occur per the Schedule of Activities (Section 2.2). On-study visits may be completed within 207 days of day 1. The date of the first dose of protocol-required therapies is defined as day 1 for cohorts 1-6, and the first dose of AMG 598/placebo after randomization for cohort 7. All subsequent doses and study visits will be scheduled based on the day 1 date. The final investigational product dose occurs on day 57.

For Cohorts 2, 4, and 6, liraglutide dosing begins on day 1 and continues through day 84. For Cohort 7, subjects will remain on 3 mg liraglutide SC QD for the duration of the study (6 months prior to screening through EOS).

Upon permanent discontinuation from the study treatment for any reason, a safety follow-up visit will be performed approximately 30 (+3) days after the end of the last dosing interval of AMG 598/placebo. End of Study visit procedures should be performed at the safety follow-up visit.

9.1.3 End of Study

End of Study (EOS) visit procedures will be performed per the Schedule of Activities (Section 2.2). For subject completing the study, this visit occurs on day 207. If feasible, all EOS procedures should be performed at the final visit for subjects who are removed from study prior to day 207.

9.2 Description of General Study Assessments and Procedures

The sections below provide a description of the individual study procedures for required time points.

9.2.1 General Assessments

9.2.1.1 Informed Consent

All subjects or their legally authorized representative must sign and personally date the IRB/IEC approved informed consent before any study-specific procedures are performed.

9.2.1.2 Demographics

Demographic data collection including sex, age, race, and ethnicity will be collected in order to study their possible association with subject safety and treatment effectiveness. Additionally, demographic data may be used to study the impact on biomarkers variability and pharmacokinetics of the protocol-required therapies.

9.2.1.3 Medical History

A complete medical history will be obtained at screening by the investigator or designated site physician. Medical history will include information on the subject's current health, psychiatric, and surgical history. Relevant medical history findings will be recorded in the subject's source notes and on the appropriate pages of the CRF. Any unresolved medical history will be graded according to Clinical Adverse Event Severity Grading Scale and is described in Section 12.4.

9.2.1.4 Physical Examination

Physical examination, including periodic neurologic examinations, will be performed as per standard of care. Physical examination findings should be recorded on the appropriate CRF (eg, medical history, event). The neurological exam will include peripheral sensory and motor evaluation, and assessment of gait, pain, position, strength and reflexes.

9.2.1.5 Physical Measurements

Height [in centimeters] should be measured without shoes. Subjects should be in a clinic gown and without shoes each time body weight [in kilograms] is measured. Body Mass Index should be calculated using the following formula: BMI (kg/m²) = weight (kg)/[height (cm)/100]^2.

Waist circumference will also be measured (cm) per the Schedule of Activities. Subjects should be standing and relaxed, with restrictive clothing removed from the abdomen. Waist circumference measurements should be taken directly on the skin with a tension-sensitive, non-elastic tape. The tape should be placed in a horizontal line around the abdomen at the level of the iliac crest. The measurement should be read at the end of a normal respiratory expiration.

9.2.1.6 Substance Abuse History

Obtain a detailed history of prior and/or concurrent use of alcohol, drugs of abuse and tobacco.

9.2.2 Efficacy Assessments

This section is not applicable.

9.2.3 Safety Assessments

Planned time points for all safety assessments are listed in the Schedule of Activities see (Section 2.2).

9.2.3.1 Adverse Events

9.2.3.1.1 Time Period and Frequency for Collecting and Reporting Safety Event Information

9.2.3.1.1.1 Adverse Events

The adverse event grading scale to be used for this study will be the Clinical Adverse Event Severity Grading Scale and is described in Section 12.4.

The investigator is responsible for ensuring that all adverse events observed by the investigator or reported by the subject that occur after the first dose of AMG 598/placebo through the end of study are reported using the Event CRF.

9.2.3.1.1.2 Serious Adverse Events

The investigator is responsible for ensuring that all serious adverse events observed by the investigator or reported by the subject that occur after the informed consent through end of study are reported using the Event CRF. All serious adverse events will be collected, recorded and reported to the sponsor or designee within 24 hours, as indicated in Section 12.4. The investigator will submit any updated serious adverse event data to the sponsor within 24 hours of it being available.

9.2.3.1.1.3 Serious Adverse Events After the Protocol-required Reporting Period

There is no requirement to monitor study subjects for serious adverse events following the protocol-required reporting period or after end of study. However, these serious adverse events can be reported to Amgen. Per local requirements in some countries, investigators are required to report serious adverse events that they become aware of after end of study. If serious adverse events are reported, the investigator is to report them to Amgen within 24 hours following the investigator's knowledge of the event.

Serious adverse events reported outside of the protocol-required reporting period will be captured within the safety database as clinical trial cases and handled accordingly based on relationship to investigational product.

The method of recording, evaluating, and assessing causality of adverse events and serious adverse events and the procedures for completing and transmitting serious adverse event reports are provided in Section 12.4.

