Males and females aged 18 to 65 years (inclusive) at the time of randomization with a BMI of \geq 30.0 and \leq 40.0 kg/m². Females enrolled in cohorts 1-6 must be of non-reproductive potential.

For cohort 7, subjects must additionally have been receiving liraglutide at 3.0 mg QD, SC for at least 6 months before screening, with liraglutide being generally well tolerated per the investigator's discretion (and subjects plan to continue liraglutide 3.0 mg QD, SC).

For a full list of eligibility criteria, please refer to Section 6.1 to Section 6.4.

Treatments

Cohorts 1, 3, and 5: After completion of all pre-dose procedures on the day of dosing, subjects will receive AMG 598 (70, 210, or 420 mg) or placebo SC on days 1, 29, and 57.

Cohorts 2, 4, and 6: After completion of all pre-dose procedures on the day of dosing, subjects will receive AMG 598 (70, 210, or 420 mg) or placebo SC Q4W x3 on days 1, 29 and 57 in addition to liraglutide SC QD. Subjects will start the first dose of liraglutide (0.6 mg SC QD) on day 1 and increase the dose of liraglutide by 0.6 mg dose increment every 7 days, up to the full dosage of 3.0 mg by week 5 and remain on 3.0 mg until day 84, inclusive (See Table 3-1).

Cohort 7: Subjects that have been on a stable dose of liraglutide (3.0 mg SC QD) for at least 6 months will continue to receive liraglutide (3.0 mg SC QD) and receive one dose of placebo SC on day -28, as part of a 4-week run-in. After completion of all pre-dose procedures on the day of dosing, subjects will then receive AMG 598 420 mg or placebo SC Q4W on days 1, 29, 57 in addition to the liraglutide (3.0 mg SC QD).

Procedures

Screening:

For cohorts 1-6, after informed consent is obtained, all screening procedures and tests establishing eligibility will be performed within 28 days before first dose of AMG 598 or placebo (day 1).

Subjects in cohort 7 will be screened between days -56 and -29 from first dose of AMG 598 or placebo (day 1). Subjects who meet all the screening inclusion/exclusion criteria will be eligible to report to the research facility on day -28, subjects enrolled will receive a dose of placebo.

Day -2:

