Serum pregnancy test at screening and EOS

^j Urine pregnancy test

^k Serum FSH Test (female only) for postmenopausal status confirmation

¹ Local laboratory at screening, then central lab at other timepoints

^mOptional in-house residency day -1 to 1 (1 night), days 6 to 8 (2 nights with +/- 1 day start window), day 62 to 64 (2 nights with +/- 1 day start window)

ⁿ DXA scan may be performed within 3 days prior to day 1 or within ±3 days of day 85 and 169 visits

Activity	Screening	Run-in			Treatm	ent		Follow up		EOS	
Study Day	-56 to-29	-28	1	15	29	57	71	85	145	207	
Visit Windows		±2 days		±2 days	±1 day	±1 day	±3 days		±7 days		
General and Laboratory Assessments											
Informed Consent	Х)	10000	1	1		1				
Medical History	Х	1	1	.0		1	1		Real and	-	
Demograhics	Х		Deres 1	1		1		1	A		
Physical Examination	Х	1	Xac		Xª	Xª	-	X		X	
CSSRS + PHQ9	Х	X	Xª		Xª	Xª		Х		X	
Body Weight	Х	x	Xª	X	Xª	Xª	Х	Х	X	Х	
Height	Х	1	1	0	1	1	1	1000	1.000		
Body Mass Index	Х		1		1	1	1	-	-		
Waist Circumference			Xª	1	Xª	X°	1	X	X	Х	
Vital Signs (BP, HR, RR, TEMP)	Х	x	Xª	X	Xª	Xª	X	X	X	Х	
12-Lead ECG ^d	Х	Х	Xª		Xª	Xª		X	A REAL PROPERTY.	Х	
Concomitant Medications	4									-	
Adverse Event Recording			4								
Serious Adverse Event Recording	4					_				_	
Clinical Chemistry ^{6,1}	X	1	Xª	And in case of	Xª	Xª	-	X	X	X	
Clinical Hematology ^{6,1}	X	1	Xª	1	Xª	Xª		X	X	X	
Coagulation Tests	X		1	Participant.	1	1		1000	1		
eGFR ^{s1}	X	1	X°	11000	T. In	1	1	-	-	х	
Serum CTX and P1NP ^{e1}	A COLUMN TWO IS NOT	1	Xª	X	Xª	Xª	X	X	x	X	
Serum Amylase and Lipase ^{6,1}	I Company of the owner of		X ^a	X	Xª	Xª	X	X	X	x	
Urinalysis®	х			1	-	1					
Alcohol, Continine and Drug Screen®	X	0	1	1	1	1	1			T C	
HIV, HBcAb, HBsAg, and HepCAb ^e	X		Jone and	1	Property of	1	1		-		
Pregnancy Test ^{an}	Xª	1	Xha	1	Xna	Xne		Xn	X	Xª	
Serum FSH Test (Females Only)	X	-	A	-		~				6	
Dosino					_	_	_				
Study Drug Administration (SC)		X	X	-	х	X	-		1		
Liraglutide (SC) ⁶			A		X	~		-			
PK and Other Blood Samples					A						
Serum PK [®]		1	X°	X	X°	X=	X	X	X	-	
Plasma PK	1		X=	X	X°	Xª	X	X	X	x	
Plasma PD (Insulin, C-peptide, Glucose, GIP,	1		A	A.	~	~	Λ.	~	-	Ś	
GLP-1, and Glucagon)er			Xe	x	X°	X°	х	X		X	
Serum PD (FFA)		-	X=	X	X°	X=	X	X	-	X	
Lipid Panel (total cholesterol, LDL-C, HDL-C	·	1		1			~	-	1	A	
and triglycerides) ⁶³	x		Xª		Xª	Xª	x			x	
HbA1c ^a	X	-	X°	-	~	~	A	X	-	A	
Pharmacogenetic	A		Xe		-	-	-	A	-		
Biomarker Development		-	Xe	-	-			v	-		
		-	X°	-	X°	-		X	- V		
Anti-AMG 598 Antibody			A		A	-		Х	X	Х	

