Imaging		-	1	-	-	-	-		1	_	
Whole body DXA scan [®]			X ^h	and the second s		1	-	X			

Table 2-3. Schedule of Activities for Cohort 7

ECG = electrocardiogram; DXA= Dual-Energy X-ray absorptiometry

^a Pre-dose assessments

^b Subjects to remain on liraglutide 3mg SC QD throughout duration of the study

^c Physical exam to include neurological assessment

^d Single ECG

^e Analyzed at the central laboratory

^f 10-hour fasting is required at all timepoints

[figure not shown]
^g Serum pregnancy test at screening and EOS for all female subjects

^h Urine pregnancy test for female subjects of reproductive potential

ⁱ Serum FSH Test (female only) for postmenopausal status confirmation

^j All subjects receive placebo injection

^k Whole body DXA scan may be performed within 3 days prior to day 1 or within ±3 days of day 85 visit

AMOEN

CONFIDENTIAL

3. Introduction

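### Cohort 7 has no single consistent start for recording non-serious adverse events, and the SAP does not tie treatment-emergence to the randomised day 1 dose

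*Protocol*

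**What the plan says.** **The run-in injection.** In the protocol synopsis (Treatments, Cohort 7), subjects stay on liraglutide and "receive one dose of placebo SC on day -28, as part of a 4-week run-in". Table 2-3 marks the study drug row at day -28 as well as at days 1, 29 and 57. Its footnote j reads "All subjects receive placebo injection"; the anchor is lost in the extracted table, but it fits the day -28 injection.

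**Start of recording.** Section 9.2.3.1.1.1 covers adverse events "that occur after the first dose of AMG 598/placebo through the end of study are reported using the Event CRF". For serious events, Section 9.2.3.1.1.2 covers those observed by the investigator or "reported by the subject that occur after the informed consent through end of study are reported using the Event CRF". In Table 2-3, as extracted, the "Adverse Event Recording" arrow for non-serious events begins in the day 1 column. The arrows for serious events and concomitant medication begin at screening.

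**Statements that point to a longer window.** The synopsis says that all adverse events are collected throughout the study, up to the end-of-study visit. Section 8.2.1 begins "Reasons for removal of a subject from the run-in period are", and its list includes an adverse event.

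**SAP.** Section 5 defines investigational product as AMG 598 or placebo and does not exclude the run-in injection. The TEAE definition, Study Day 1 and the safety set (Section 6.1) all depend on the first dose of that product.

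**The concern.** A subject can have a protocol injection, develop a non-serious event within the next four weeks and even be removed from the run-in because of it, with no clear requirement to enter the event on the Event CRF. About 30 sites enrol into cohort 7, and the protocol gives them signals that differ.

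Two things are at stake. The first is the pre-treatment record. Safety is the primary objective, and Section 3.3.3.1 expects that the combination may worsen the gastrointestinal effects of liraglutide. The run-in shows those effects on liraglutide plus placebo, in the same subjects, before randomised treatment. Events not collected then cannot be recovered later.

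The second is classification. If the SAP is programmed as written, the treatment-emergent period in cohort 7 opens four weeks before randomised treatment.

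**Working it through.** **1. Length of the run-in.** Protocol Section 5.3.2 gives 28 days of screening, 28 of run-in and up to 207 on study: 28 + 28 + 207 = 263 days. This reproduces the stated 263.

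**2. Which dose starts reporting in Section 9.2.3.1.1.1?** The phrase there carries no qualifier, so it could mean the day -28 placebo. Four other places use it for the randomised dose:
- the synopsis counts cohort 7 screening back from the first dose of AMG 598 or placebo and labels that dose day 1;
- Section 9.1.1 names the run-in placebo separately from AMG 598/placebo;
- Section 9.1.2 defines cohort 7 day 1 as "the first dose of AMG 598/placebo after randomization for cohort 7";
- Section 6.6, just after describing run-in failures, speaks of subjects who leave before receiving AMG 598/placebo. That makes no sense if the run-in injection counts.

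The better reading is therefore day 1, as in Table 2-3.

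**3. What that reading leaves out.** The period from the run-in injection to the last visit is 28 + 207 = 235 days. Non-serious events have no recording requirement for 28 of them: 28 / 235 = 11.9%. For the 60 randomised subjects this is 28 × 60 = 1,680 subject-days. Run-in failures would add to it.

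**4. Against the rest of the protocol.** A day 1 start contradicts the synopsis, because cohort 7 subjects are enrolled after screening (Section 6.6) and are therefore in the study during the run-in. It also sits badly with Section 8.2.1, which acts on adverse events that nothing clearly requires to be recorded.

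**5. Against the SAP.** The cohort 7 anchors side by side:

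| Item | Protocol | SAP, read literally |
|---|---|---|
| Day 1 | first randomised dose (9.1.2) | first day of any IP, so day -28 (Section 5) |
| Safety set | IP received on day 1 (10.2.1.1) | any IP dose, so run-in placebo qualifies (6.1) |
| Randomisation | day 1 (7.2) | day -28 (Section 5, Enrollment Date) |
| TEAE | used but not defined | begins or worsens after the initial IP dose, so from day -28 (Section 5) |

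The general baseline definition (SAP Section 5) and the final analysis set (SAP Section 6.5) inherit the same anchor. So does the imputation of some partial or missing start dates to the first dose (SAP Appendix A).

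**6. Consequence.** Taken literally, the SAP counts treatment-emergent events from day -28, while Table 2-3 records non-serious ones from day 1. A serious run-in event would be collected and counted as treatment-emergent; a non-serious one would generally be absent. Subjects who had only the run-in injection would enter the safety set.

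**The case against.** The strongest reply is that the protocol is coherent on its own terms. A reader might infer a direct contradiction, with Section 9.2.3.1.1.1 starting on day -28 and Table 2-3 on day 1. The documents do not force that, as step 2 shows. The arrow position also comes from a broken table, so it should not carry much weight alone.

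A reader might also infer that run-in events go wholly unrecorded. That is too broad. Serious events are reported from consent, concomitant medication is tracked from screening, and subjects removed from the run-in have an early termination visit (Section 6.6). Criterion 112 calls for a day 1 evaluation that includes medical history, and Section 9.2.1.4 sends examination findings to the CRF.

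On classification, investigators must record onset dates (Appendix 4), and TEAE status uses a CRF flag for events starting after the first dose. Both arms have the same run-in and background liraglutide, so the concurrent placebo arm separates background events from drug effect. Starting non-serious collection at the randomised dose is a defensible choice.

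Most of this stands. It does not remove three things:
- The synopsis still says otherwise.
- The day 1 evaluation may pick up an ongoing finding but not reliably an episode that has resolved. Table 2-3 schedules medical history only at screening, and Appendix 4 counts as adverse events conditions first detected after study treatment even if they were present earlier.
- The TEAE flag is only as good as the dose it refers to, and the SAP does not say which dose that is for cohort 7.

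**Conclusion.** The point holds as an inconsistency to be reconciled and a gap in collection. Non-serious adverse events in the cohort 7 run-in are not clearly required on the Event CRF, against the synopsis and awkwardly with Section 8.2.1. The SAP's first-dose anchor, taken literally, is day -28 rather than the randomised dose.

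The size is 28 days per subject, or 1,680 subject-days for 60 subjects. This describes the length of the window and says nothing about how many events fall in it. It rests on the day 1 reading of Section 9.2.3.1.1.1 and on the arrow position in the extracted Table 2-3.

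A reader might infer that cohort 7 TEAE rates or a risk ratio will be distorted by a calculable amount. The documents do not support a figure: they give no run-in event rate or misentry rate, the adverse event analysis is descriptive, and no risk ratio is planned. The window precedes randomised treatment and is the same in both arms, so the randomised comparison stays unbiased by design. No sample size or detection probability changes. What is gained is a pre-treatment adverse event record and correct TEAE classification.

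**What to change.** **Protocol.** For cohort 7, start adverse event recording at the day -28 injection in Table 2-3 and say so in Section 9.2.3.1.1.1. The synopsis and Section 8.2.1 then fit the rule. The recording window from the first protocol injection becomes 235 days instead of 207.

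**SAP.** For cohort 7, anchor TEAE, Study Day 1 and the safety set to the first randomised dose on day 1, in line with protocol Sections 9.1.2 and 10.2.1.1. Apply the same anchor to the general baseline definition, the final analysis set and the date imputation in Appendix A, and correct the cohort 7 randomisation day. List run-in adverse events separately, and count as treatment-emergent only onset or worsening after the day 1 dose.

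**Cost.** Wording changes in both documents and a small amount of extra data entry at visits that already take place: day -28, day 1 and, where it applies, the early termination run-in visit. No new visit or procedure is needed.
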